Appendix

SAP 2.1

The SAP was amended on Feb 6, 2023 to correct an error in the primary analysis in SAP 2.0 which stated that pre-surgery pupil response to acute experimental pain would be entered into a three way interaction with study drug and preferred cognitive style to predict modeled recovery from pain after lower extremity total joint arthroplasty. As stated in the NIH application which funded the research, the IRB approved protocol for the study and its analysis, and the ClinicalTrials.gov registration, the primary analysis was stated to use pre-operative resting pupil diameter rather than its response to pain. The error in the SAP was observed prior to performing the primary analysis and is described in this amendment.

Addition of pre-surgery pupil response to acute experimental pain as a 4th interacting factor was inferred in the grant application and protocol and the SAP is amended to include this as a pre-planned secondary analyses from this extensive dataset, in addition to creating a unique subset of questionnaire questions to predict postoperative pain intensity trajectory, assessing the day to day time relationship between pain and disability during recovery, the role of anesthetic technique in long term recovery, and interrogating various biomarkers for speed of trajectory of recovery after surgery.

SAP 2.2

The SAP was amended a second time on April 26, 2023 to correct an error in the primary and secondary analyses to remove the statements that modeled trajectory of change in outcome measures for each analysis (pain in the primary; daily steps, disability scores, and opioid use in the secondaries) would be adjusted for preoperative values of these measures. Such adjustments were not included in either the IRB approved protocol nor the NIH application which funded the study and its analysis.

There is a large literature demonstrating a positive correlation between the extent of pain catastrophizing with pain, disability, and opioid use and a negative correlation with activity. Since the cognitive construct to be used in both the primary analysis and the secondary analyses is derived from the pain catastrophizing instrument, adjustment of modeled trajectories by preoperative pain, activity disability, and opioid use would be expected to diminish the independent effect of the cognitive construct in these analyses. The adjustments in modeling using these preoperative variables were intended as sensitivity analyses rather than testing the primary and secondary hypotheses. This mistake was identified and this amendment was prepared and submitted prior to performing analyses using these adjustments.

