Study period	Screen	Baseline	In hospital	Daily diaries	Follow up 1	Follow up 2	Phone	Orthopaedic clinic visits
Visit number	0	Visit 1			Visit 2	Visit 3		
Week		-4 to -2*	0-3 days	0-8	8	26	12,16,20,52	2, 6, 12-16, 26, 52
Informed consent		X						
Demographic		X						
Medical/surgical history		X						
Questionnaires		X			X	X		
Pain testing & pupillometry		X						
Randomisation		X						
Study drug dispensing		X						
In hospital pain/medication data & disposition			X					
Daily diary & accelerometry		X		X				
Phone assessment of pain, medication use, function							X	
Joint function								X

*Study medication begins at -2 weeks and continues until 3 weeks after surgery

Final analysis of the gabapentin vs placebo comparison with and without inclusion of interactions with preferred cognitive style and pre-surgery pupil responses to pain will take place when all patients have completed the 12-month follow-up and data for the primary endpoint have been cleaned, which occurred in May 2022. Results were anticipated to be posted by Jan, 2023, but complexities associated with generation of a novel psychologic construct from the final dataset and defining parameters for pupil assessment prevented completion of the primary analysis until Mar, 2023.

15. *Timing of outcome assessments*

The schedule of study procedures is provided in the protocol and summarized in the table below.

Section 4: Statistical Principles

16. *Level of statistical significance*

All applicable statistical tests will be 2-sided and will be performed using a 5% significance level.

17. *Adjusting for multiplicity*

The primary analysis involves a single model-based inference that will be interpreted at the 5% threshold of statistical significance. If the primary analysis is significant, each main factor, all two way interactions, and the three way interactions will be evaluated and each will be interpreted at the 5% level of significance with no adjustments made for multiplicity.

18. *Confidence intervals*

All confidence intervals presented will be 95% and two-sided.

19a. *Definition of adherence to the intervention and how it is assessed*

Compliance is assessed based on the number of daily diary entries after hospital discharge. It is defined as:

$$\% \text{ compliance} = (\text{number of entries}/\text{number of days entries were to be completed}) * 100\%$$

19b. *How adherence will be presented*

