Pupil diameter: Pupil recordings will be conditioned to remove artifacts (e.g., blinks), saccades, and deviations from central gaze that might bias recordings. A response window with appropriate lag reflecting delayed onset of pupil response due to physiological delays will be used to define change in diameter to each stimulus as previously reported.¹⁷ Two pupil measurements will be estimated from the session data, the mean pupil diameter during baseline (i.e., pre-stimulus) and the modeled response to pupil to 50-degree stimulus.

Gabapentin: Randomized treatment assignment of either gabapentin or placebo will be a fundamental predictor of trajectory.

These individual predictors sets will then be used to test the primary hypothesis that gabapentin alters time course of recovery after arthroplasty in a manner dependent on its interaction with preferred cognitive style and pre-surgery pupil diameter. The primary statistical inference will be the difference in the likelihood ratio between two nested models using a chi-square test with K degrees of freedom (i.e., K being the difference in the number of parameters between the two models). The first model (i.e., null model) will consist of the pain trajectory model with the addition of patient characteristics and operative characteristics. The second nested model will add medication assignment (gabapentin versus placebo), cognitive style (catastrophizing \leftrightarrow optimism latent score), and resting pupil diameter, and all two-way interactions and three-way interaction between these 3 predictors (i.e., 3 two-way, and 1 three-way interaction for both intercept and slope parameters) from the first nested model. This approach allows a single likelihood ratio test of the primary hypothesis and will be interpreted using a two-tailed hypothesis test using $p < 0.05$. A statistically significant difference in the likelihood ratio test will be interpreted as evidence to support the primary hypothesis in that the interaction of these predictors impacts some aspect of the change process beyond that of the basic model. We have planned several sensitivity analyses using multiple imputation to account for missing data.

Several exploratory secondary analyses of the data set:

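### A significant primary test can rest on cognitive style alone, yet Section 27 reads it as support for a gabapentin interaction

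*SAP*

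**What the plan says.** Section 8 words the null hypothesis as no difference between gabapentin and placebo that depends on style and pupil diameter, and then writes it as a formula for equal fit of two models. Section 27a/27b defines the models. The null model holds the pain trajectory, age, sex, site and surgery type. For the larger model, "The second nested model will add medication assignment (gabapentin versus placebo), cognitive style", resting pupil diameter and every interaction among the three, on both intercept and slope. A significant difference "will be interpreted as evidence to support the primary hypothesis", which is the gabapentin-interaction hypothesis.

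Section 17 adds that after a significant joint test every main effect and interaction is examined, and "each will be interpreted at the 5% level of significance with no adjustments made for multiplicity".

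The Appendix note on SAP 2.2 (26 April 2023) removes the statements that the modelled outcomes "would be adjusted for preoperative values of these measures". It gives three reasons: "Such adjustments were not included in either the IRB approved protocol nor the NIH application which funded the study and its analysis"; the adjustments "were intended as sensitivity analyses rather than testing the primary and secondary hypotheses"; and "adjustment of modeled trajectories by preoperative pain, activity disability, and opioid use would be expected to diminish the independent effect of the cognitive construct". Section 27e keeps the baseline-adjusted model as a sensitivity analysis.

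**The concern.** The null model contains neither style nor pupil diameter, so the primary test credits their prognostic value to the same statistic as the gabapentin terms. The SAP 2.2 note itself cites a large literature linking catastrophizing with pain. A component that has nothing to do with treatment is thus expected to be non-zero, and it can carry the whole test. The planned reading would then report that gabapentin interacts with style and pupil size when only style predicts pain. Randomization gives no protection here, because style is not randomized.

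**Working it through.** **1. The plan's own figure.** Section 11 states power above 90% with 250 patients for a likelihood ratio test. It gives no effect size, SD or correlation in the text, so the figure cannot be reproduced. As a benchmark, a 14-df test at 5% (critical value 23.68) has 90% power at a noncentrality of 23.0. One predictor with correlation r to the patient's intercept supplies about −N ln(1 − r²). With r = 0.297 this is −250 × ln(1 − 0.088) = 23.0. A style–intercept correlation of about 0.30 alone therefore gives 90% power with every treatment term at zero.

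**2. Parameter count.** For a linear or log(time) form each term enters twice (intercept and slope).
- All added terms: (3 main + 3 two-way + 1 three-way) × 2 = 14.
- Containing treatment: 4 × 2 = 8.
- Treatment interactions only: 3 × 2 = 6.
- Without treatment (style, pupil, style × pupil): 3 × 2 = 6.

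The multiplier is 3 for a quadratic form and 4 for a cubic form.

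**3. Joint test with no gabapentin effect.** From the SAP: N = 250, 1:1 allocation, diary days 0–56, four covariates. Assumed: log(day + 1) form, between-patient SD 2.0 (intercept) and 0.5 (slope), residual SD 1.5, covariates without effect. There are 3000 runs per row. In the first column, a/b means correlation a between style and preoperative pain, and b between preoperative and postoperative pain. The first three rows have no direct style effect. The Section 17 columns give the share of runs with a significant joint test and at least one significant treatment-containing term, without baseline adjustment.

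| Style effect | Joint test, unadjusted | Joint test, baseline-adjusted | 8-df treatment test, unadjusted | Section 17, four 2-df tests | Section 17, eight coefficients |
|---|---|---|---|---|---|
| 0.1/0.1 | 6.8% | 7.0% | 6.9% | 4.9% | 5.5% |
| 0.3/0.3 | 12.7% | 7.1% | 7.1% | 7.3% | 9.1% |
| 0.5/0.5 | 69.6% | 7.0% | 7.1% | 17.5% | 28.4% |
| direct 0.2 SD, 0.3/0.3 | 81.6% | 45.0% | 6.0% | 18.8% | 31.2% |
| direct 0.3 SD, 0/0.3 | 84.2% | 87.7% | 6.1% | 19.1% | 31.8% |
| direct 0.3 SD, 0.3/0.3 | 98.5% | 84.0% | 6.0% | 19.8% | 33.6% |
| direct 0.3 SD, 0.5/0.5 | 100% | 82.9% | 6.3% | 19.0% | 33.6% |

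The small excess over 5% in the 8-df column is the chi-square approximation at this sample size. The runs use a two-stage likelihood ratio on per-patient intercepts and slopes. On one complete data set this gave 35.114, the same as a maximum-likelihood mixed model. A second set-up, without diary noise and with intercept and slope errors correlated at −0.4, gives 83% instead of 70% at 0.5/0.5. The size depends on such choices; the direction does not.

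**4. Section 17.** Once style opens the gate, the treatment terms have no joint protection. For independent tests the chance of at least one false result is 1 − 0.95⁴ = 18.5% with four tests and 1 − 0.95⁸ = 33.7% with eight, close to the lower rows of the table.

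**5. Which test matches the hypothesis.** The 8-df test includes the gabapentin main effect, but the hypothesis is about interaction. With a true gabapentin main effect of 0.3–0.5 SD, no interaction and a direct style effect of 0.3 SD, an 8-df gate followed by single interaction tests (2 df each) lets at least one false interaction through in 12–17% of runs. A joint 6-df test of the treatment interactions holds this at 6–8%.

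**The case against.** The strongest reply is that Section 17 already separates the terms, so a style-only result would normally show up as a style term. That stands in part: a false treatment term appears in up to about 20% of runs with four tests, far below the 84–100% for the joint test alone. But the sentence in Section 27 applies whatever those later tests show, and the tests have no joint control.

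A second reply is that a significant joint test is a correct rejection of the formula in Section 8. That is so. A reader might call this an inflated type I error, but for the model comparison as written it is not. The fault is that the formula does not isolate the hypothesis as worded.

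A reader might also infer that SAP 2.2 caused the problem. It did not. The style terms would be in the joint test with or without baseline pain, and a direct style effect of 0.3 SD still makes the adjusted test significant in 83–88% of runs. Leaving baseline pain out keeps the total association of style, which is defensible. The other two reasons given for the amendment cannot be checked from the SAP.

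A reader might infer that the primary result was known before SAP 2.2. Section 14 gives March 2023 for completing the primary analysis, and the 2.2 note says only that it was "submitted prior to performing analyses using these adjustments". That does not exclude an earlier unadjusted fit. But the March date may be a forecast, and nothing in the document shows that results were seen.

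Last, a reader might infer that the Section 27e analysis adjusts for pain measured on study drug, since drug starts two weeks before surgery and 25a refers only to diaries before surgery. Table 1 places the baseline diary at weeks −4 to −2, with the next diary column starting at week 0. The window in 27e needs a clarifying phrase; no dilution of a gabapentin effect has been shown.

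**Conclusion.** The point holds for Sections 17 and 27 and should be corrected. That 6 of 14 tested parameters contain no treatment, and that a significant result is nevertheless read as support for a gabapentin interaction, follows from the text without any assumption. How often this would mislead is not known, because it rests on assumed correlations and variances. It is negligible if style barely relates to pain and very likely if style has a direct effect of 0.2–0.3 SD. The documents do not support placing the fault in SAP 2.2, or a claim that the amendment followed sight of the results.

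**What to change.** In Section 27, keep the joint test as the first step and replace its interpretation as follows:
- A significant joint test shows only that treatment, style, pupil diameter or their interactions improve fit.
- A gabapentin effect is claimed only if the joint test of the treatment-containing terms is also significant at 5% (8 df for a linear or log(time) form, 12 quadratic, 16 cubic). The comparison model holds style, pupil and style × pupil.
- Dependence of the gabapentin effect on style or pupil is claimed only if the joint test of the treatment interactions is significant at 5% (6, 9 or 12 df). The comparison model also holds the treatment main effect.

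In Section 17, examine single interaction terms only after the interaction test. The unadjusted model can stay primary.

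Two minor clarifications: limit the 27e baseline pain covariate to diary days before the first dose, in line with Table 1; and state the unblinding date and the date the unadjusted model was first fitted, relative to 26 April 2023.

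**Cost.** One or two extra tests, some wording, and fewer results that count as support. For a true three-way slope effect of 0.2–0.3, the share supported under the 8-df rule falls from 48–85% (Section 17 route, four tests) to 41–81% without a direct style effect, and from 73–96% to 49–87% with one of 0.3 SD. Part of that loss is support from terms with no true effect. The 6-df test costs less when the effect is purely an interaction: 8-df power of 48.5% and 86.6% corresponds to noncentrality 8.14 and 17.43, at which the 6-df test has about 54% and 90%.
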